3. INTERIM ANALYSIS AND DATA MONITORING COMMITTEE REVIEW

An independent DMC will review safety and efficacy data periodically. Safety review starts once the first 10 subjects complete their week 12 visits. Efficacy review takes place at interim analysis when at least 60% of subjects complete their Week 26 MMTT assessment. After each review, the DMC is to make recommendations regarding the continuation of the study as planned or, in the event that any unanticipated concerning safety events or issues occur, placing the study on hold or stopping the study. In addition, the DMC roles and responsibilities, and the general procedures (including communications) are defined and documented in the DMC charter developed by the sponsor detailing the safety data monitoring and efficacy data review to be conducted by the DMC.

An administrative interim analysis was performed when at least 60% of subjects complete their Week 26 MMTT assessment. The interim endpoint of interest is the MMTT-stimulated 4-hour C-peptide AUC. A mixed model for repeated measures (MMRM) was fitted on the post-baseline $\log(\text{AUC}+1)$ data. Similar analyses were conducted on the extended interim analysis set to leverage the external placebo subject data. All adverse event data up to the interim analysis cut-off date was also reviewed in the interim analysis. Refer to interim analysis SAP for interim analysis details.

After interim analysis review, the committee recommended the efficacy analysis supporting the IA be provided by the SSG for review in subsequent scheduled DMC meetings before study unblinding. The objective was to re-evaluate the observation at IA. The details regarding these reviews were provided in the DMC SAP and DMC Charter.

4. SUBJECT INFORMATION

Unless specified otherwise, full analysis set will be used for the subject information analyses and subjects will be analyzed according to the treatment group to which they were randomized at Week 0, regardless of the treatment they actually received. The number of subjects in each analysis set will be summarized by treatment group and overall.

Simple descriptive statistics, such as mean, median, standard deviation, interquartile range, maximum, and minimum for continuous variables, and counts and percentages for discrete variables will be used to summarize most data and no formal statistical analyses for treatment comparisons will be performed. In addition, subject listings will also be used to present the data.

4.1. Demographics and Baseline Characteristics

Demographic (age, race, sex, height, weight and BMI) and baseline characteristic variables will be summarized by randomized treatment groups and overall (all treatments pooled together) for

all subjects randomized. Descriptive statistics (N, mean, SD, median, and range) will be provided for continuous variables at baseline as well as the number and percentage of subjects for categorical variables.

Baseline disease characteristics to be summarized will include but not limited to: number of days since diagnosis of T1D, fasting blood glucose prior MMTT, 4-h peak C-peptide, 4-h C-peptide AUC, 2-h C-peptide AUC, HbA1C, insulin use unit per day, and subjects positive to at least one diabetes-related autoantibody.

In addition, the number and percentage of subjects in the following categories will be summarized by treatment group:

- Age :<12 years, 12-18 years, >18 years
- Weight: <45 kg, ≥45 kg
- Number of positive diabetes-related autoantibodies: 1, >1-≤3 and >3
- Type of positive diabetes-related autoantibody: GAD-65, IA-2, ZnT8, ICA, and insulin
- Baseline HbA_{1c}: ≤6.5%, >6.5%
- Number of days since diagnosis of T1D: < 60, ≥60

4.2. Disposition Information

Subjects who discontinued study agent prior to Week 52 along with the reasons for discontinuation will be summarized by treatment group. In addition, subjects who terminated study participation prior to Week 52 along with the reasons for termination will be summarized by treatment group for all subjects who received at least one administration of study agent.

4.3. Treatment Compliance

Study agent compliance will be summarized descriptively through Week 52 for the safety analysis set. Number of subjects by randomized treatment versus actual treatment will be presented in a summary table.

4.4. Extent of Exposure

The number and percentage of subjects receiving study agent will be summarized by treatment group for the safety analysis set. Descriptive statistics will be presented for the following parameters:

- Number of administrations
- Total duration of exposure

Total duration of exposure is defined as the time lapses between the first and last study admissions.

4.5. Protocol Deviations

Major protocol deviations will be tabulated by treatment group as defined in the following categories:

- Entered but did not satisfy criteria
- Developed withdrawal criteria but not withdrawn
- Received a disallowed concomitant treatment
- Received wrong treatment or incorrect dose
- Other

4.6. Prior and Concomitant Medications

Prior medications will be summarized by the number of subjects taking pre-specified categories of by treatment group. Prior medications are defined as any therapy used before the day of first dose (partial or complete) of study agent. Concomitant medications are defined as any therapy used on or after the same day as the first dose of study agent, including those that were started before and continued after the first dose of study agent. Concomitant medications will be listed.

5. EFFICACY

5.1. Methods of Analysis

All efficacy analyses will be performed on the full analysis set unless otherwise specified. The full analysis set includes all randomized subjects who have received at least 1 dose of study agent. The primary efficacy endpoint will be analyzed by using a mixed model for repeated measures (MMRM). Assessment of the primary efficacy endpoint on the PP analysis set will be conducted as the supportive analysis.

5.2. Analysis Specifications

5.2.1. Level of Significance

Unless otherwise specified, all statistical testing procedures will be performed at a 2-sided significance level of 0.05.

5.2.1.1. Multiplicity Adjustment for Testing Procedures

To control for multiplicity in the primary endpoint analysis and major secondary endpoint analyses, the hypothesis testing will be conducted in a hierarchical manner with the test on the primary analysis first and the tests on major secondary analyses next. The success of any major secondary analysis, i.e., $p\text{-value} < 0.05$, is contingent upon the success of the primary statistical analysis. Hochberg approach will be applied within major secondary endpoint analyses.

Nominal p-values will be reported for all other efficacy endpoints.

5.2.2. Data Handling Rules

The following missing data handling rules will be applied to the analyses in this study. For the analyses of change from baseline for a given efficacy parameter, only subjects who have both baseline and at least one post-baseline measurement for that parameter will be included.

5.2.2.1. Missing Data

Unless otherwise specified, in situations with the presence of missing data (e.g. lost to follow-up, missed study visit) the following rules will apply:

Missing baseline value: No imputation will be performed for missing baseline values.

Subjects missing values for any subgroup parameters (defined in Section 2.4) at baseline will be excluded from the subgroup analysis.

Continuous endpoints:

- In general, no imputation will be performed for missing post-baseline continuous values. Missing data will be adjusted for in the statistical model (i.e. Mixed effect Model Repeated Measures)
- In several sensitivity analyses of the primary endpoint, missing C-peptide AUC value will be imputed through linear extrapolation. More specifically, missing $\log(\text{AUC}+1)$ value will be imputed through a random effect model with time (continuous), age, treatment, and treatment by time interaction as fixed effects, and intercept and slope at subject level as random factors.
- Multiple Imputation (MI) is applied in one sensitivity analysis of the primary endpoint.

Binary endpoints:

- In general, subjects with missing observations of interest at a visit will be regarded as non-responders for that visit.
- When evaluating sustained response status for C-peptide AUC, if a subject presents one or more intermittent missing C-peptide AUC value, then the response statuses at visits prior to and after the miss value(s) will be referred to. If the subject is a responder at both visits, the he/she will be regarded as a responder at the missing visit. If the subject is a responder at the visit prior to the missing value and a non-responder at the visit after missing value(s), then the subject becomes a non-responder at the first missing visit. If all C-peptide AUC values after a visit are missing, then the response status for those missing visits is set to be non-responder.

Time-to endpoints:

- For time-to peak C-peptide < 0.2 pmol/mL, in case of intermittent missing measurement, if both the previous value and the next observed value are ≤ 0.2 , then the missing value is regarded as ≤ 0.2 . Otherwise, treat the first missing value above 0.2.
- Similarly, for time-to loss of remission (remission duration), in case of intermittent missing measurement, if both the previous and the next observed value are ≤ 9 (in remission), then the missing value is regarded to be ≤ 9 . Otherwise, treat the first missing value above 9.

5.2.3. General Analysis Method

Data summaries will be provided for each treatment group. Statistical comparisons will be made between active and placebo treatment groups.

Descriptive statistics such as mean, median, standard deviation, minimum, and maximum will be used to summarize continuous variables. Counts and percentages will be used to summarize categorical variables. Recurrence data will be summarized by mean as well as counts and percentages. Median will be reported for time to event variables. Graphical data displays (e.g., mean plots, Kaplan-Meier curves, and forest plots) will be used to support the presentation of data.

5.3. Primary Efficacy Endpoint

5.3.1. Definition

The primary endpoint is the MMTT-stimulated 4-hour C-peptide AUC at Week 52.

Four-hour C-peptide AUC is calculated as the standardized trapezoidal summation. It is calculated as the AUC based on available c-peptide concentration values from the MMTT divided by the time span between 0 minute (baseline) and the time associated with last available c-peptide concentration. The 4-hour MMTT should take 250 minutes to perform with blood samples collected at 11 time points: – 10, 0, 15, 30, 60, 90, 120, 150, 180, 210, and 240 minutes. As the peak concentration is expected to be within 60 to 180 minutes, the AUC value is considered invalid and set to missing if no C-peptide concentration is measured during this time period (60 minutes through 180 minutes, inclusive).

5.3.2. Analysis Methods

In the primary efficacy analysis, data from all randomized subjects will be analyzed according to their assigned treatment group regardless of the actual treatment received. The primary efficacy analyses are based on the full analysis set. To address the primary objective of the study, the primary endpoint will be analyzed by using a MMRM based on restricted maximum likelihood. No missing data handling rules will be utilized for this analysis. The model will be based on a normalizing transformation of $\log(\text{AUC}+1)$. The analysis will use post-baseline $\log(\text{AUC}+1)$ as the response variable and will include the fixed, categorical effects of treatment, time, gender and treatment-by-time interaction, as well as the continuous, fixed covariates of baseline,

baseline-by-time and age. The baseline will be in $\log(\text{AUC}+1)$ scale as well. An unstructured covariance will be used to model the within-patient errors. The Kenward-Roger approximation was used to estimate denominator degrees of freedom and adjust standard errors. The treatment comparison at Week 52 in terms of the least square mean difference and the 2-sided 95% confidence interval (CI) will be estimated based on this model. Descriptive statistics and estimates from the above model will be presented on the back-transformed scale. Specifically, the back-transformed mean is the geometric-like mean derived through $\exp(y)-1$, where $y = \log(\text{AUC}+1)$. For transparency and completeness, descriptive statistics on the raw scale will be presented as well. Nominal p-values for treatment comparison will be provided for reference.

In addition, the estimated LS means of change from baseline in $\log(\text{AUC}+1)$ scale over time as well as the corresponding 60% and 95% CI from the mixed effect model will be provided by treatment group. Plot of Mean treatment difference at week 52 in change from baseline in $\log(\text{AUC}+1)$ scale will be also provided. Plot of mean 4-h C-peptide AUC by treatment group will be shown over time as well as plot of the individual 4-h C-peptide AUC over time.

5.3.2.1. Subgroup Analysis for the Primary Endpoint

The treatment difference of the primary endpoint by each subgroup factor listed in Section 2.3 will be explored and presented through forest plots. Subgroup analysis will not be performed on the sensitivity analyses described below.

5.3.2.2. Sensitivity Analysis

To test the robustness of the primary analysis results, sensitivity analyses will be conducted. The following sensitivity analyses will be performed:

In sensitivity analysis 1, the primary endpoint will be analyzed using the same model as in the primary analysis on **per-protocol population**, which is defined as all subjects in the full analysis set with exclusion of subjects identified by the study physician according to the blinded list of subjects with major protocol deviations that may potentially confound the primary efficacy endpoint.

In the sensitivity analysis 2, a random effect model will be fit with $\log(\text{AUC}+1)$ at all time points (including baseline) as the response variable, age, gender, time (continuous variable), treatment and treatment by time interaction as fixed effects, interception and slope as random effects. As time is a continuous effect, the study day of the C-peptide collection is used as time. No missing imputation is needed.

In sensitivity analysis 3, an analysis of covariance (ANCOVA) model with $\log(\text{AUC}+1)$ at Week 52 as the response variable, baseline $\log(\text{AUC}+1)$ and age as covariates, and treatment as a fixed factor will be performed. Missing data handling strategy of multiple imputation will be implemented. Missing values will be imputed through Markov chain Monte Carlo (MCMC)

method. The analysis results based on each of the $N = 10$ imputed datasets will be pooled together to estimate treatment effects and test treatment difference at Week 52.

In sensitivity analysis 4, an analysis of covariance (ANCOVA) model with $\log(\text{AUC}+1)$ at Week 52 as the response variable, baseline $\log(\text{AUC}+1)$, gender and age as covariates, and treatment as fixed factors will be performed. Missing data handling strategy of linear extrapolation will be implemented.

In sensitivity analysis 5, comparing change from baseline in 4-hour C-peptide AUC by using non-parametric method rank analysis of covariance. For subjects with missing Week 52 value, the missing measurement will be imputed with linear extrapolated value.

In sensitivity analysis 6, constrained Longitudinal Analysis will be applied with $\log(\text{AUC}+1)$ including baseline as the response variable, the fixed, categorical effects of treatment, time, and treatment-by-time interaction, as well as the fixed covariate of age.

In sensitivity analysis 7, a similar model as in the primary analysis will be applied with covariates identified by a stepwise regression model on C-peptide AUC in $\log(\text{AUC}+1)$ scale at Week 52. The covariates in the stepwise regression will include sex, race (white, or not white), number of positive T1D related autoantibodies (≤ 3 , >3), age, baseline weight, baseline HbA1c, number of days since diagnosis at randomization, and baseline C-peptide AUC in $\log(\text{AUC}+1)$ scale. For subjects with missing Week 52 value, the missing measurement will be imputed with linear extrapolated value.

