1.4. Sample Size Justification

This study is designed to enroll approximately 81 subjects in order to have sufficient power to detect a difference between the golimumab groups and the placebo group for the primary efficacy endpoint. The rationale for the study sample size is based on the hypothesis tests for the primary efficacy endpoint.

The sample size calculation is based on the primary endpoint, an MMTT 4-hour C-peptide AUC at Week 52. Due to skewed C-peptide AUC data, normalizing transformation of $\log(AUC + 1)$ is

applied for sample size assessment. The method has been well accepted and used in numerous clinical studies. Based on published data, a common standard deviation (SD) of log (AUC+1) of 0.215 is assumed, and the back-transformed means for 4-hour C-peptide AUC are assumed to be 0.385 and 0.635 for the placebo and golimumab groups respectively, ie the expected treatment difference (back-transformed) is 0.25. Based on these assumptions, with 81 subjects (54 on golimumab and 27 on placebo), there is 90% power to detect a treatment difference with a 2-sided significance level of 0.05 through a 2-sample t-test.

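### Sensitivity analyses 4 and 5 appear to analyse a single model prediction of a missing Week 52 value as if it were measured, which understates their uncertainty

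*SAP*

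**What the plan says.** SAP 5.2.2.1 provides that in several sensitivity analyses of the primary endpoint a "missing C-peptide AUC value will be imputed through linear extrapolation". It then defines the term: the missing log(AUC+1) "value will be imputed through a random effect model with time (continuous), age, treatment, and treatment by time interaction as fixed effects", with intercept and slope as subject-level random factors. The same section limits multiple imputation to one sensitivity analysis.

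SAP 5.3.2.2 applies the rule as follows:

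- **Analysis 4** is an ANCOVA at Week 52 adjusted for baseline, gender and age: "Missing data handling strategy of linear extrapolation will be implemented".
- **Analysis 5** is a rank analysis of covariance on change from baseline. For a missing Week 52 value, "the missing measurement will be imputed with linear extrapolated value".
- **Analysis 7** first selects covariates by stepwise regression on Week 52 log(AUC+1), then fits a model similar to the primary one. Its imputation sentence is worded as in analysis 5 and comes after the description of the stepwise step.
- **Analysis 3**, by contrast, is an ANCOVA on 10 MCMC-imputed datasets with pooled results.

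The primary MMRM (SAP 5.3.2) uses no imputation.

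**The concern.** A model prediction differs from a measurement in two ways: it has no residual scatter, and it carries the error of the fitted parameters. Because the prediction model contains treatment-by-time, each imputed value also follows the fitted trend of its own arm. An ANCOVA that counts such values as data sees too little residual variance and too many independent observations, so its standard error is too small.

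The SAP introduces these analyses as a test of robustness. If analyses 4 and 5 reject more often than their nominal level, their agreement with a positive primary result is weaker evidence than it looks. Nothing in the plan would tell a reader to discount it.

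**Working it through.** **1. The plan's own figure.** The SAP assumes that "a common standard deviation (SD) of log (AUC+1) of 0.215 is assumed" and that the back-transformed means "are assumed to be 0.385 and 0.635 for the placebo and golimumab groups respectively" (SAP 1.4).

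- Difference on the log scale: ln(1.635) − ln(1.385) = 0.1659.
- Standard error: 0.215 × √(1/54 + 1/27) = 0.0507.
- Normal approximation: Φ(0.1659/0.0507 − 1.96) = 90.6%. The noncentral t with 79 df gives 89.9%.

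This reproduces the statement that "with 81 subjects (54 on golimumab and 27 on placebo), there is 90% power to detect a treatment difference". The split 54 + 27 = 81 contains no stated allowance for missing data.

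**2. Simulation under no treatment effect.**

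- From the documents: 54:27 subjects, MMTT at screening/baseline and Weeks 12, 26, 38 and 52, SD 0.215, and the rule that "all statistical testing procedures will be performed at a 2-sided significance level of 0.05" (SAP 5.2.1).
- Assumed: the missing rate, its timing, and two settings of within-subject correlation (higher and lower).
- Method: fit the SAP 5.2.2.1 model by REML, replace each missing Week 52 value once by its prediction, then run the ANCOVA (analysis 4) and rank ANCOVA (analysis 5). There were 2,000 replicates per setting, so the Monte Carlo SE is about 0.5 points near 5%.

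The table shows results with missingness spread over visits. Ranges cover the two correlation settings.

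| Week 52 missing | Analysis 4 type I error | Analysis 5 type I error | Analysis 4 reported SE ÷ true SD |
|---|---|---|---|
| 5% | 5.3-5.6% | 5.6-5.7% | 0.98 |
| 10% | 6.2-6.3% | 6.1-7.4% | 0.95 |
| 15% | 7.4-8.3% | 8.4-8.5% | 0.89-0.91 |
| 20% | 8.1-8.3% | 8.4-9.0% | 0.87-0.89 |
| 30% | 11.1-12.3% | 11.6-12.6% | 0.80-0.83 |

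With no missing data the ANCOVA held 5.0-5.1%. If only the Week 52 visit is missed, analysis 4 gave 5.4-6.3% at 10% missing and 6.4-7.8% at 20%.

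**3. Does the small SE explain the inflation?** If the reported SE is a fraction r of the true SD, a test with critical value about 1.99 (76 df) rejects with probability near 2[1 − Φ(1.99r)].

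- r = 0.98 gives 5.1%.
- r = 0.95 gives 5.9%.
- r = 0.87 gives 8.3%.
- r = 0.80 gives 11.1%.

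These are close to the simulated rates, so the understated SE accounts for most of the excess.

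**4. Stochastic imputation from the same model.** The comparator for analysis 4 used 20 draws with parameter and residual noise, pooled by Rubin's rules. Its mean SE was 1.01-1.06 times the true SD at 10-20% missing. Type I error was 4.0-4.9% there and 3.4-4.9% across all settings. Pooling of the rank statistic in analysis 5 was not simulated.

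**5. Analysis 7, if the extrapolated value enters the final MMRM.** This was approximated with the primary covariates and no stepwise step, at 20% missing, with 358 replicates. Mean SE was 0.0332 against a true SD of 0.0360, a ratio of 0.92. Type I error was about 6.4%, with a Monte Carlo SE of about 1.3 points, so that rate alone is not distinguishable from 5%. Without imputation the SE ratio was 0.0381/0.0364 = 1.05.

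**The case against.** - **Single imputation is inferred.** The SAP does not say how many values are drawn. This stands as a reason to ask for clarification. But the SAP confines multiple imputation to one analysis and spells out datasets and pooling only for analysis 3, so a single prediction is the natural reading.
- **The missing rate is unknown and may be low.** This also stands. At 5% missing the excess is within simulation error. Protocol 10.2 asks subjects who stop treatment to keep attending, so stopping treatment need not mean a missing Week 52 value. On the other side, SAP 5.3.1 sets the AUC to missing when no sample falls between 60 and 180 minutes, so an attended visit can also yield a missing value.
- **A reader might infer that three of the seven analyses are affected.** The text does not establish this. The imputation sentence in analysis 7 may serve only the stepwise regression, which needs a Week 52 value, and the primary model it resembles uses no imputation.
- **A reader might infer a biased treatment effect or an unsafe primary result.** Neither is supported. The shortfall shown is in the standard error, and the primary MMRM is not imputed. The hierarchy in SAP 5.2.1.1 covers only the primary and major secondary analyses, and no decision rule uses analyses 4, 5 or 7.
- **Protocol 11.3 calls for varied missing-data strategies, and analysis 3 already uses multiple imputation.** Variety is a sound aim. It should come from different assumptions, not from leaving imputation error out of the standard error. The examples that Protocol 11.3 names for the ANCOVA are a completers' analysis and multiple imputation.

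**Conclusion.** The point holds for analysis 4 (standard error, interval and p-value) and for analysis 5 (p-value; the SAP specifies no interval for it). Its size depends on a missing rate that the documents do not give. With missingness spread over visits, the SE in analysis 4 is too small by about 2% at 5% missing, 5% at 10%, 11-13% at 20% and 17-20% at 30%. The effect is negligible near 5% missing, material from about 10-15%, and smaller if only the Week 52 visit is missed. These figures also rest on the assumed correlation settings and on the reading that each missing value is predicted once. Analysis 7 is an open question of wording. The consequence is overstated robustness, and the primary test is not in error.

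**What to change.** - **Analyses 4 and 5:** keep the random-slope model, but impute several times, drawing parameters, subject effects and residuals. Pool analysis 4 by Rubin's rules. Rubin's rules do not apply directly to a rank test statistic, so pool analysis 5 by a suitable method, such as combining standardised test statistics.
- **Analysis 7:** state whether the extrapolated value is used only in the stepwise selection or also in the final MMRM. If only in selection, run the final MMRM on observed data. If also in the final model, apply the same multiple imputation there.
- **Minimum alternative:** label the affected p-values and intervals as ignoring imputation uncertainty.

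The cost is SAP wording, modest programming (somewhat more for the rank analysis) and wider intervals in analysis 4. In the simulation its mean SE rose from 0.0347 to 0.0372 and from 0.0456 to 0.0501 at 10% missing (ratios 1.07 and 1.10). At 20% it rose from 0.0335 to 0.0383 and from 0.0434 to 0.0522 (ratios 1.14 and 1.20). Analysis 4 would also move closer to analysis 3, differing mainly in the imputation model and the gender term.

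Rerunning the draws with a delta shift for golimumab subjects with missing data would probe missing-at-random. That is a separate, optional addition.

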A target of approximately 81 subjects will be randomly assigned in a 2:1 ratio to receive golimumab or placebo, administered SC for 52 weeks and monitored for an additional 52 weeks. Subjects will be randomized to receive active therapy (golimumab) or placebo and be stratified based on a C-peptide AUC of < 0.66 pmol/mL or ≥ 0.66 pmol/mL from a 4-hour MMTT conducted at study screening.

All randomized subjects will receive a total of 27 doses of study agent, either active treatment or matched placebo, administered SC every 2 weeks (q2w). Study subjects weighing < 45 kg who are randomized to active treatment will receive an induction dose of golimumab 60 mg/m^2 SC at Weeks 0 and 2 followed by a maintenance dose of 30 mg/m^2 SC at Week 4 and q2w through Week 52. Study subjects weighing ≥ 45 kg who are randomized to the golimumab treatment group will receive an induction dose of golimumab 100 mg SC at Weeks 0 and 2 followed by a maintenance dose of golimumab 50 mg SC at Week 4 and q2w through Week 52. Subjects randomized to the placebo treatment group will receive a SC placebo injection q2w through Week 52 to match the active arm (Figure 1). The protocol will give the option for study agent administration by subject or caregiver outside of the study site, ie, self-administration, after proper training (see Section 6).

Following randomization and the 52-week treatment period, there will be a 52-week off-therapy follow-up period focused on determining the off-therapy durability of the effect of golimumab. Thus, the participation for each subject is 104 weeks.

There will be a number of study visits that will include extensive metabolic assessments including a 4-hour MMTT. These assessments will occur at screening, during the double-blind treatment period (Weeks 12, 26, 38, and 52), and the off-therapy monitoring period (Weeks 78 and 104). The primary endpoint analysis will be derived from data obtained at the double-blind Week 52 visit (double-blind period). During the open-label extension period, a 4-hour MMTT will be performed during OL screening (unless performed < 3 months ago), OL Week 28, and OL Week 52. For C-responders who are lacking the necessary information to calculate IDAA1c score, an HbA1c will be performed and 10 days of insulin dose information will be required. Data from these and other visits will contribute to other key efficacy and safety endpoints and provide pharmacokinetic and exploratory assessments.

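### SAP sensitivity analysis 6 is named a constrained longitudinal analysis, but its listed fixed effects do not impose the common baseline mean that defines one

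*SAP*

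**What the plan says.** SAP 5.3.2.2 introduces the analysis by name: "In sensitivity analysis 6, constrained Longitudinal Analysis will be applied with" the transformed AUC. The rest of the sentence sets out the response and the model terms: "including baseline as the response variable, the fixed, categorical effects of treatment, time, and treatment-by-time interaction, as well as the fixed covariate of age". Nothing more is specified for it. There is no statement that baseline means are equal across arms, no covariance structure and no contrast.

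The primary model in SAP 5.3.2 handles baseline differently. Its response is post-baseline only, and baseline enters on the right-hand side: "as well as the continuous, fixed covariates of baseline". Its interaction with time, and age, are also in that model. Its estimand is explicit: "The treatment comparison at Week 52 in terms of the least square mean difference". The same section also asks for a plot of the Week 52 treatment difference in change from baseline on the log(AUC+1) scale.

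Sensitivity analysis 2, in the same SAP section, also puts baseline in the response alongside treatment and treatment-by-time, and is not called constrained. The sensitivity analyses listed in Protocol 11.3 do not include a constrained longitudinal model, so the protocol does not settle the question.

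**The concern.** The purpose of a constrained longitudinal model is to treat baseline as an outcome while requiring the randomised arms to share one baseline mean. On complete data that requirement gives the Week 52 comparison the same baseline adjustment as ANCOVA. Without it, the model is the ordinary unconstrained longitudinal model. Its Week 52 mean difference then carries no baseline adjustment on complete data, and its change-from-baseline contrast is a plain change-score comparison.

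A programmer who codes the terms as listed gets the second model under the name of the first. The result would be less precise than intended and would move with any chance baseline difference. If it then disagreed with the primary result, a reader could not tell a real lack of robustness from the lost adjustment.

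**Working it through.** **Inputs.** From SAP 1.4: "a common standard deviation (SD) of log (AUC+1) of 0.215 is assumed"; "the back-transformed means for 4-hour C-peptide AUC are assumed to be 0.385 and 0.635 for the placebo and golimumab groups respectively"; and "with 81 subjects (54 on golimumab and 27 on placebo), there is 90% power to detect a treatment difference", two-sided alpha 0.05. From Protocol 3.1: MMTTs at screening (the baseline) and Weeks 12, 26, 38 and 52, so 5 times. Assumed, because the documents give no value: the baseline-to-Week 52 correlation r, taken as 0.5 to 0.74 with a wider range also shown; equal SD at both times; no dropout; age ignored.

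**1. The plan's own figure.** Effect = log(1.635) − log(1.385) = 0.1659. SE = 0.215 × √(1/54 + 1/27) = 0.0507. Power = Φ(0.1659/0.0507 − 1.96) = 0.906, or 0.899 from the noncentral t with 79 df. The stated 90% reproduces, so these inputs are a sound base.

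**2. Does the term list leave the baseline difference free?** Two arms × 5 times = 10 means. Listed terms: 1 (intercept) + 1 (treatment) + 4 (time) + 4 (treatment-by-time) = 10 parameters. The mean model is saturated, so the baseline arm difference is a free parameter. A constrained model has 5 (time) + 4 (treatment by post-baseline time) = 9. The single age covariate does not alter this count.

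**3. What each model estimates.** In one simulated complete dataset (54:27, r = 0.7, unstructured covariance, maximum likelihood):
- Literal model: treatment main effect −0.0020, equal to the observed baseline difference; Week 52 difference 0.2138, equal to the unadjusted difference; change contrast 0.2158, equal to the change-score difference.
- Constrained model: 0.2157, equal to ANCOVA on baseline.

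**4. Precision.** With SE₀ = 0.0507:
- constrained: SE₀ × √(1 − r²)
- literal, Week 52 difference: SE₀
- literal, change from baseline: SE₀ × √(2(1 − r))

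The ratios to the constrained SE are 1/√(1 − r²) and √(2(1 − r))/√(1 − r²).

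| r (assumed) | Constrained SE | Literal Week 52 SE | Literal change SE | Ratio, Week 52 | Ratio, change |
|---|---|---|---|---|---|
| 0.3 | 0.0483 | 0.0507 | 0.0600 | 1.05 | 1.24 |
| 0.5 | 0.0439 | 0.0507 | 0.0507 | 1.15 | 1.15 |
| 0.6 | 0.0405 | 0.0507 | 0.0453 | 1.25 | 1.12 |
| 0.7 | 0.0362 | 0.0507 | 0.0393 | 1.40 | 1.08 |
| 0.74 | 0.0341 | 0.0507 | 0.0365 | 1.49 | 1.07 |
| 0.9 | 0.0221 | 0.0507 | 0.0227 | 2.29 | 1.03 |

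**5. Sensitivity to a baseline difference.** A chance imbalance of +0.05 on the log(AUC+1) scale shifts the literal Week 52 difference by r × 0.05, which is +0.025 at r = 0.5 and +0.035 at r = 0.7. It shifts the change contrast by (r − 1) × 0.05, which is −0.025 and −0.015. The constrained estimate does not move.

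**The case against.** The strongest reply is that the SAP does name the method. The constraint is a restriction on parameters, not a model term. The same list with the arm difference set to zero at baseline is the constrained model, and an experienced programmer may impose this in code without being told. That stands. A reader might infer that an unconstrained analysis is planned, or that the constraint has been deliberately removed. The documents do not support that; they show only that the constraint is named and not written out.

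A reader might also infer that baseline adjustment is lost altogether. That depends on a contrast the SAP does not give. SAP 5.3.2 shows interest in change from baseline, and a change contrast would still subtract baseline, at the smaller cost in the last column of the table.

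Two mitigations are fair. Randomisation is stratified on baseline C-peptide AUC at 0.66 pmol/mL (SAP, Randomization), a cut that Protocol 3.2.1 expects to lie near the median. This limits imbalance in the variable at issue but does not eliminate it. The supporting set also already contains baseline-adjusted checks: analysis 1 reuses the primary model, 3 and 4 are ANCOVAs on baseline, and 7 is a variant of the primary model. A correctly constrained analysis 6 would agree closely with these on complete data, so little robustness evidence hangs on it.

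Finally, the absence of gender from analysis 6 might be read as a second error. It is not: analysis 3 omits gender too, and a sensitivity analysis may use different covariates from the primary model.

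**Conclusion.** The specification of sensitivity analysis 6 is internally inconsistent. It names one model and lists the fixed effects of another, and no other text in the SAP or protocol resolves the difference. The parameter count (10 against 9) needs no assumption about the data.

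The size of the consequence is conditional on three things: that the list is fitted literally, which contrast is taken, and the assumed correlation. For r from 0.5 to 0.74 the standard error is 15–49% larger than under the constrained model for the Week 52 mean contrast, or 7–15% larger for change from baseline. These figures also assume equal variances, complete data and no age effect; adjusting for age could move the relevant correlation either way.

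The reach is small. This analysis carries no alpha and is outside the testing hierarchy in SAP 5.2.1.1. The primary analysis, its significance level and the sample size are unaffected. It is a wording correction worth making, not a threat to the trial's conclusion.

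**What to change.** Replace the sentence for sensitivity analysis 6 in SAP 5.3.2.2 with a full specification:

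- response: baseline and post-baseline log(AUC+1);
- fixed effects: time (categorical), treatment by post-baseline time with the arm difference fixed at zero at baseline, and age;
- covariance: unstructured within subject;
- contrast: treatment difference at Week 52, with its 95% confidence interval.

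Adding gender or the Kenward-Roger adjustment, to match the primary model, is optional. The cost is one sentence of SAP text. No data collection, sample size or primary-analysis change follows.
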